3.3 Sample Size Estimation

3.3.1 Primary Calculation

A sample size of 118 subjects (59 in each group) provides 88% power to detect a hazard ratio of 2.0 for the time to treatment failure comparing the group randomized to discontinue adalimumab to the group randomized to continue using adalimumab, assuming a median time until treatment failure of 10 weeks in the group that discontinues adalimumab (Arm 1) and of 20 weeks in the group that continues on adalimumab (Arm 2), an equal allocation between groups, and a 10% total loss to follow-up.

For sample size planning, we use the approximate formula given in Friedman et al (2010) for the number in each group:

$$N = \frac{(Z_\alpha + Z_\beta)^2 (\phi(\lambda_C) + \phi(\lambda_I))}{(\lambda_I - \lambda_C)^2}$$

Where λ denotes the rate in the intervention arm (λ_I) and control arm (λ_c), $\phi(\lambda) = \lambda^2 / 1 - e^{-\lambda T}$ at censoring time T , and Z_α, Z_β are quantiles from the standard normal distribution at power (1- β) and significance level α .

In a retrospective study by our group of JIA-associated uveitis patients on immunomodulatory therapies (antimetabolites, cyclosporine, TNF- α inhibitors, or combination therapy), 37% of patients attempted to stop treatment after achieving corticosteroid-sparing control of inflammation.²³ Of patients who stopped TNF- α inhibitors, nearly 50% experienced a recurrence of inflammation within 100 days after stopping treatment. Approximately 80% of patients had a recurrence of ocular inflammation within one year after stopping treatment.

Furthermore, a retrospective study of uveitis patients on infliximab showed that patients with JIA-associated uveitis who attempted to stop anti-TNF- α therapy after achieving control of inflammation experienced recurrence of inflammation after a median of 76 days.²⁴ Similarly, in a small retrospective study outside our group, 6 pediatric uveitis patients flared between 3 and 7 months after discontinuing adalimumab.²⁵ Based on these data, we can expect to observe a majority of treatment failures within the first 6 months and nearly all treatment failures by Month 12 among patients randomized to discontinue adalimumab treatment. It is important to note that stopping infliximab treatment involves a gradual taper of the dose over the course of several weeks. In both studies, time to recurrence of inflammation was measured from the start of the taper rather than the point at which patients had completely stopped the medication. Because discontinuing adalimumab treatment does not involve a taper in our trial, we expect the time to recurrence of inflammation to be shorter as compared to infliximab. Therefore, we anticipate time to treatment failure of 10 weeks in patients randomized to discontinue adalimumab in ADJUST.

Table 3. Previous time-to-event uveitis studies

Author	Population	Median Time to Uveitis Relapse
Acharya et al. (2018)	JIA-associated uveitis patients who discontinued TNF- α (n = 11)	100 days
Shakoor, Esterberg, & Acharya (2014)	JIA-associated uveitis patients who discontinued infliximab (n = 18)	76 days

Castiblanco, Meese, & Foster (2016)	Uveitis pediatric patients who discontinued adalimumab	3 to 7 months (range)
-------------------------------------	--	-----------------------

In a clinical trial of JIA-associated uveitis patients with active inflammation on a stable dose of antimetabolite, 114 patients were randomized to adalimumab or placebo biweekly subcutaneous injections and followed for up to 18 months.²⁶ The mean duration of sustained inactive disease was 179.3 ± 16.9 days in the adalimumab treatment group (vs. 14.5 ± 23.9 days in the placebo group). An open label long-term follow-up study of non-infectious adult uveitis patients treated with adalimumab demonstrated that, among patients with inactive disease who entered the study, over 90% of patients still had inactive disease at week 54.²⁷ At 78 weeks, 74% still had inactive disease.²⁸ Given the available evidence on disease recurrence for patients on long-term adalimumab treatment, we can expect a lower recurrence rate and longer time to treatment failure in patients continuing on adalimumab compared to those discontinuing treatment. While these studies suggest that most uveitis patients on adalimumab remain inflammation-free greater than one year, we have conservatively estimated 20 weeks to be the median time to treatment failure among patients randomized to continue adalimumab treatment.

Thus, 118 patients total (59 per group), provides 88% power to detect a hazard ratio of 2.0 for the time to treatment failure, assuming a 10% loss to follow-up. We assume an alpha of 0.05 (two sided). Adjusting for country in our analyses is assumed to give us even greater power. A power table is provided in Table 4 below, varying the median time until treatment failure (in weeks).

Table 4: Total Sample Size Based on Median Time to Treatment Failure for Stopping vs. Continuing Adalimumab

		80% Power	90% Power
Stopping Treatment Versus Continuing Treatment	8 weeks vs 16 weeks	92	124
	10 weeks vs 20 weeks	96	126
	12 weeks vs 24 weeks	98	130

3.3.2 Power for Subgroup Analyses and Other Analyses

Our primary analysis is powered at 88% and most secondary analyses are reported at 80% power.

3.3.2.1 Specific Aim 1

Planned Secondary Analyses

- **Time to treatment failure, with censoring at 6 months.** We anticipate 80% power to detect a hazard ratio of 2.0 between randomization groups, based on 118 subjects (we anticipate same loss to follow up of 10%).
- **The proportion of people with uveitis flares over 6 months.** For sample size planning, we assume a test of proportions between the two randomization groups. Based on prior research, we expect 70% of those who discontinue adalimumab to experience flare by 6 months.²⁴ We anticipate 80% power to detect a difference of 28% between the groups, based on 118 subjects. Note that we anticipate fewer flares in the continuation group, but the test will be two-sided at alpha of 5%.
- **The proportion of people with uveitis flares over 12 months.** Based on prior research, we expect about 80% of those who discontinue adalimumab will have a uveitis flare by 12 months.²⁴ With our total sample size of 118 and the assumed 10% loss to follow-up by 12 months, with 80% power, we anticipate a power to detect a difference of 28% in the flare rate between the groups.

Planned Secondary Analyses with Alternative Outcomes

- **Longitudinal BCVA.** For sample size assessment, we assume a T-test comparing change scores between the two randomization groups. We assume a standard deviation of 0.59, based on prior research.²⁹ The total sample size of 118 and the assumed 10% loss to follow-up by 12 months provides 80% power to detect a difference of 0.32 logMar.
- **The CHAQ score.** For sample size planning, we assume a T-test comparing change scores between the two randomization groups. We shall assume a standard deviation of 23 based on prior research.³⁰ Thus with the total sample size of 118 and the assumed 10% loss to follow-up by 12 months, with 80% power we can detect a difference of approximately 13 points.
- **The EQ-5D-Y score.** For sample size planning, we assume a T-test comparing change scores between randomization groups. Assuming a standard deviation of 17.3,³¹ the total sample size of 118 and assumed 10% loss to follow-up by 12 months provides over 80% power to detect a mean difference of 7.9 points.
- **The CVFQ score.** For sample size planning, we assume a T-test comparing change scores between the randomization groups. Assuming a standard deviation of 1.70 based on a validation study of the CVFQ,³² a total sample size of 118 and assumed 10% loss to follow-up by 12 months provides 80% power to detect a mean difference of 0.93 points.
- **The EYE-Q score.** For sample size planning, we assume a T-test comparing change scores between the randomization groups. Assuming a standard deviation of 0.75,⁸ the total sample size of 118 and assumed 10% loss to follow-up by 12 months provides approximately 80% power to detect a mean difference of 0.41 points.

- **The JADAS-10 score.** As before, we use a T-test comparing change scores between the two groups for sample size planning. Assuming a standard deviation of 8.23,¹⁰ the total sample size of 118 and assumed 10% loss to follow up by 12 months provides approximately 80% power to detect a mean difference of 4.5 points.
- **The JADAS-27 score.** Similarly, assuming a standard deviation of 8.16,¹⁰ the sample size of 118 and assumed 10% loss to follow-up by 12 months provides approximately 80% power to detect a mean difference of 4.5 points.
- **The ADA levels.** Assuming a standard deviation in ADA levels of 10,³³ the total sample size of 118 (and, the 10% assumed loss to follow-up by 12 months) suggest approximately 80% power to detect a difference of 5.5 in ADA serum levels in $\mu\text{g/mL}$.
- **The proportion of people with arthritis flares.** We assume (for sample size assessment) a test of proportions between the two randomization groups. Based on prior research, we expect 1% of those who continue adalimumab to have a flare by 6 months.²⁶ We anticipate 80% power to detect a difference of approximately 16% in the proportion of individuals experiencing arthritis flares among those who discontinue adalimumab (assuming a total sample size of 118 and 10% loss to follow-up by 12 months).
- **The proportion of patients who achieve an improvement in JADAS-10.** Assuming that 85% of those continuing on adalimumab will have an improvement in JADAS-10 score from baseline,³⁴ a total sample size of 118 (and 10% assumed loss to follow-up) provides approximately 80% power to detect a difference of at least 26% in the proportion of patients achieving an improvement between treatment groups.
- **The proportion of people with macular edema.** We anticipate at most 1% of the individuals continuing treatment to develop macular edema, given its absence at baseline. We anticipate approximately 80% power to detect a difference of 15% (in absolute terms) in macular edema in the discontinuation arm (given 118 subjects).

The analyses for censoring at 6 months are similar to 12 months, with small decreases in detectable effect sizes due to assuming slightly shorter follow-up by month 12.

3.3.2.2 Specific Aim 2

Specific Aim 2 is exploratory, and is hypothesis generating. However, we present selected power analyses to illustrate the sufficiency of the sample size of the trial—fixed in Specific Aim 1—to inform regression models of the exploratory outcomes in Specific Aim 2.

For modeling the effect of the potentially predictive biomarker MRP8/14, we assume a

median split as a guide to power. Assuming approximately 50 uveitis flares among our patient population, we anticipate 80% power to detect a difference in MRP8/14 levels of 140 ng/ml (assuming a standard deviation of 250 ng/ml, based on previous studies).^{35,36}

For modeling the number of missed study treatment doses in the first 12 months, we anticipate over 80% power to detect a difference of 2.8 missed doses between the discontinuation and continuation groups (assuming 118 patients enrolled, and a standard deviation of 5).

For the time to failure outcome within 12 months, we anticipate 88% power to detect a hazard ratio of 2.0 between patients taking antimetabolites at baseline and those not using antimetabolites, assuming approximately equal numbers in each group (assuming 10% loss to follow-up).

3.3.2.3 Specific Aim 3

Primary Analysis

The proportion of people who achieved corticosteroid-sparing controlled ocular inflammation (Table 2) by month 6 of the study based on treatment intervention. For sample size planning, we assume a test of proportions between the two randomization groups. Based on prior research, we assume that 30% of those who discontinue adalimumab will have controlled ocular inflammation by month 6.²⁴ We anticipate over 80% power to detect a 29% difference between the two groups, based on 118 subjects.

The proportion of people who achieved corticosteroid-sparing controlled ocular inflammation by month 12 of the study based on treatment intervention. For sample size planning, we assume a test of proportions between the two randomization groups. Based on prior research, we assume that 24% of those who discontinue adalimumab will have controlled inflammation by month 12.²⁴ We anticipate approximately 80% power to detect a difference of 28% between the groups.

Secondary Analyses

Power analyses for the continuous outcomes in this Aim are similar to those in Specific Aim 1.

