Quality-of-life questionnaires Quality of life will be measured at Baseline, Month 6, Month 12 and Treatment Failure visits. Health-related quality of life (HR-QOL) will be assessed in patients 5 years and older using the Child Health Assessment Questionnaire (CHAQ). The EuroQol 5 Dimension Youth Survey (EQ-5D-Y) will also be completed by patients 4 years and older. Both of these questionnaires can be taken by patients and their caretakers. Vision-related quality of life (VR-QOL) will be assessed in patients using the Children's Visual Function Questionnaire (CFVQ) for patients aged 3-7 years and the Effect of Youngster's Eyesight on Quality of Life (EYE-Q) questionnaire for patients 5 years and older.

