2.3 Specific Aims

2.3.1 Specific Aim 1

Primary Outcome of the trial. The primary outcome for Specific Aim 1 will be time to treatment failure, with censoring at 12 months. Treatment failure occurs when recurrence of ocular inflammation is observed and/or the recurrence of joint inflammation is persistent and severe enough to necessitate unmasking to manage the arthritis recurrence. The recurrence of ocular inflammation is defined as one or more of the features in Table 1 in at least one eye:

Table 1: Criteria for Treatment Failure by Uveitis Recurrence
(at least one of the following in at least one eye)

Parameter	Definition
Anterior chamber cells*	≥2-step increase** at two separate visits ≥7 days apart >0.5+ cell observed for ≥28 days ≥3+ cell observed at a single visit
Vitreous haze***	>0.5+ haze at a single visit
Choroid & retina	Active retinal / choroidal lesions or macular edema (CST >2 standard deviations above normal thickness or cysts in 1mm central subfield) at a single visit

*SUN criteria³, **increase is based on inflammation at baseline; ***NEI vitreous haze grading scale⁴

Secondary Objectives

- To compare the proportion of people exhibiting treatment failure between the randomization groups during the first 6 months and during the first 12 months of study duration.
- To compare the cost-effectiveness of adalimumab therapy between the randomization groups during 12 months.

Secondary Objectives with Alternative Outcomes

We propose to compare longitudinal values of specific variables between the two randomization groups. The following outcomes will be compared:

- Best Corrected Visual Acuity (BCVA) score,
- Childhood Health Assessment Questionnaire score (CHAQ)⁵ in patients ages 5+,
- EuroQol 5 Dimension Youth Survey (EQ-5D-Y)⁶ score in patients ages 4+,
- Children's Visual Functioning Questionnaire (CVFQ)⁷ score in children aged 3 to 7 years,
- Effects of Youngster's Eyesight on Quality of Life (EYE-Q)⁸ score in children ages 5+,
- Juvenile Arthritis Disease Activity Score (JADAS)⁹ values: JADAS-10 and JADAS-27,
- Estimates of anti-adalimumab antibody (ADA) levels.

We also propose to compare proportions between the two randomization groups. These proportions correspond to the time until treatment failure or censoring time of 6 months as well as until treatment failure or censoring time of 12 months. Specifically:

- The proportion of patients who exhibit an arthritis flare, as defined in the Manual of Operations Section 6.4.1.²

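### The EQ-5D-Y power line in SAP 3.3.2.1 claims more than 80% power, but its own inputs give about 64%; separately, the CVFQ line counts all 118 patients for a form limited to ages 3 to 7

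*SAP*

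**What the plan says.** SAP 3.3.2.1 lists power statements for eight continuous secondary outcomes. For the EQ-5D-Y it assumes a t-test comparing change scores between arms, a standard deviation of 17.3, 118 patients and 10% loss by 12 months, and concludes that this "provides over 80% power to detect a mean difference of 7.9 points".

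For the CVFQ it uses the same test, the same 118 patients and 10% loss, and a standard deviation of 1.70, and concludes that this "provides 80% power to detect a mean difference of 0.93 points". SAP 2.3.1 defines the CVFQ outcome as the "score in children aged 3 to 7 years", and SAP 2.3.3 repeats the limit. Protocol 8.1 likewise gives the form "for patients aged 3-7 years". Protocol 5.1 admits patients from age 2, sets no upper age at enrolment, and says explicitly that patients may be older than 16.

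**The concern.** The EQ-5D-Y difference of 7.9 points is 0.457 of its stated standard deviation. The other continuous outcomes, with the same number of patients and much the same stated power, have detectable differences of 0.54 to 0.57 standard deviations. Both cannot be right at one sample size.

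The CVFQ line has a different fault. Its arithmetic is right for 118 patients, but 118 patients can supply CVFQ scores only if every one of them is aged 3 to 7.

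At stake is how a null result on these scores would be read: someone relying on the plan would think the trial could detect smaller differences than it could. The figures also carry forward, because SAP 3.3.2.3 says that power for the continuous outcomes in Aim 3 is similar to that in Aim 1.

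**Working it through.** **Inputs**
- Test, standard deviations, differences, 118 patients and 10% loss: SAP 3.3.2.1.
- Allocation 1:1: SAP 2.4.1.
- Two-sided alpha of 0.05: SAP 3.3.1 for the primary calculation, repeated in SAP 3.3.2.1 for flares over 6 months. The EQ-5D-Y and CVFQ lines do not restate it.
- Evaluable per arm: 118 × 0.9 / 2 = 53.1, taken as 53.

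**Method.** Two-sample t-test with n per arm. The noncentrality is δ = (difference / SD) × √(n/2), with 2n − 2 = 104 degrees of freedom. Power comes from the noncentral t distribution.

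**Step 1: does this method reproduce the SAP's other lines?**

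| Outcome | Difference | SD | Difference / SD | Power at 53 per arm | Difference at 80% power |
|---|---|---|---|---|---|
| BCVA (logMAR) | 0.32 | 0.59 | 0.542 | 79.0% | 0.324 |
| CHAQ | 13 | 23 | 0.565 | 82.2% | 12.6 |
| CVFQ | 0.93 | 1.70 | 0.547 | 79.7% | 0.934 |
| EYE-Q | 0.41 | 0.75 | 0.547 | 79.6% | 0.412 |
| JADAS-10 | 4.5 | 8.23 | 0.547 | 79.6% | 4.52 |
| JADAS-27 | 4.5 | 8.16 | 0.551 | 80.3% | 4.48 |
| ADA | 5.5 | 10 | 0.550 | 80.1% | 5.49 |
| **EQ-5D-Y** | **7.9** | **17.3** | **0.457** | **64.4%** | **9.50** |

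Seven of the eight lines reproduce. CHAQ comes out slightly above 80% because its difference is rounded ("we can detect a difference of approximately 13 points"). The match indicates that the SAP used two-sided 0.05 with 53 per arm and applied each standard deviation directly.

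**Step 2: the EQ-5D-Y line.**
- 7.9 / 17.3 = 0.457, and δ = 0.457 × √(53/2) = 2.35.
- Normal approximation: Φ(2.35 − 1.96) = 65.2%. Noncentral t: 64.4%.
- With SD 17.3, 80% power needs 9.5 points.
- To detect 7.9 points with 80% power needs about 77 evaluable per arm (2 × 77 / 0.9, or about 172 enrolled), or an SD of about 14.4.

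**Step 3: looser assumptions for EQ-5D-Y.**

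| Assumption | Power for 7.9 points |
|---|---|
| As stated: 53 per arm, two-sided | 64.4% |
| No loss: 59 per arm, two-sided | 69.1% |
| 53 per arm, one-sided | 75.5% |
| No loss and one-sided | 79.4% |

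None reaches 80%, and each departs from something the SAP states.

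**Step 4: the CVFQ line.** If a share f of patients is aged 3 to 7, the evaluable number per arm is 53.1 × f. The documents give no age distribution, so these shares are assumptions for illustration.

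| Assumed share aged 3 to 7 | Per arm | Power for 0.93 points | Difference at 80% power |
|---|---|---|---|
| 100% | 53.1 | 80% | 0.93 |
| 75% | 39.8 | 67% | 1.08 |
| 50% | 26.6 | 50% | 1.33 |
| 30% | 15.9 | 32% | 1.74 |

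The SAP's figure is the first row.

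**The case against.** **An unstated correlation could rescue the EQ-5D-Y line.** The SAP does not say whether 17.3 is the standard deviation of a change score or of a single visit. If it is a single-visit value, the change-score SD is 17.3 × √(2(1 − r)), which falls to the required 14.4 at a baseline correlation r of about 0.65. With baseline adjustment, which is the SAP's analysis template for continuous outcomes in 3.1.1, the SD is 17.3 × √(1 − r²), and r of about 0.55 is enough. So a reader should not infer that no interpretation reaches 80%. But no correlation is stated, the line names a t-test on change scores, and the other seven lines use their standard deviations directly. The objection narrows the claim to the inputs as the line reads. It does not make the line right.

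**The stakes have shrunk.** The monitoring committee stopped enrolment in February 2024 (Protocol 10.1.12.5; SAP 3.1.1), and the secondary outcomes chosen for interim reporting include no quality-of-life score. SAP 3.5 makes analyses after the primary one descriptive, with 95% confidence intervals that show precision directly. This stands, and it limits the consequence. It does not correct the stated figures.

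**The age argument could be stretched too far.** A reader might infer that the CHAQ and EYE-Q (from age 5) and the EQ-5D-Y ("score in patients ages 4" and over) are also materially overstated. The documents do not support that. They give no share of patients below those ages, and entry requires at least 12 consecutive months of adalimumab and of controlled inflammation. Nor would it be strictly true to call every stated power an upper bound: the CHAQ has 82% power at 13 points and keeps 80% with up to about 5% of patients under 5. The CVFQ differs because its range is closed at the top as well, while enrolment is not.

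**The size of the CVFQ shortfall is unknown.** This is correct. Only the direction is established.

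**Conclusion.** The point holds in two parts. The EQ-5D-Y power is misstated on the inputs as written: about 64% for 7.9 points, with about 9.5 points needed for 80%. This rests on 17.3 being the change-score SD, 53 evaluable per arm and a two-sided 0.05 test, the conventions that reproduce the other seven lines. The documents do not show whether 7.9 or 17.3 is a misprint.

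The CVFQ figure of 80% for 0.93 points holds only if every patient is aged 3 to 7. It is too optimistic by an amount that the documents do not allow one to fix.

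Severity is minor. A reader might infer that the trial itself is underpowered; nothing here supports that. The sample size of 118 was set on time to treatment failure and does not depend on these lines.

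**What to change.** - **EQ-5D-Y (SAP 3.3.2.1):** restate as 80% power to detect a mean difference of about 9.5 points, with 64% power for 7.9 points. If the standard deviation or the difference is a misprint, correct it instead. If a baseline correlation was assumed, state it and its source.
- **CVFQ (SAP 3.3.2.1):** restate the detectable difference for the age-eligible number, labelled as a planning range: about 1.7, 1.3 or 1.1 points if 30%, 50% or 75% of patients are aged 3 to 7.

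The cost is two lines of SAP text. No added patients, changed test or changed decision follows, and no further sentence on the age limits of the other questionnaires is needed.

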1 PROTOCOL SUMMARY

1.1 SYNOPSIS

Title:	Adalimumab in Juvenile Idiopathic Arthritis-associated Uveitis Stopping Trial (ADJUST)
Study Description:	Multicenter, block-randomized, double-masked, placebo-controlled trial to compare the safety and efficacy of stopping adalimumab treatment versus continuing adalimumab treatment in patients with uveitis associated with juvenile idiopathic arthritis (JIA) or patients with chronic anterior uveitis (CAU). 118 patients with JIA-associated uveitis or CAU, with control of ocular inflammation on adalimumab will be randomized to either continue adalimumab at their current dose or stop adalimumab. Patients will complete monthly visits for 4 months in addition to visits at 6, 8, 10, and 12 months.
Objectives:	Primary Objective: To compare time to recurrence of ocular inflammation between patients with JIA-associated uveitis or CAU, randomized to stop adalimumab treatment and patients randomized to continue treatment. Secondary Objectives: To determine predictors of JIA-associated uveitis or CAU disease recurrence. To compare 6- and 12-month outcomes between the two treatment groups.
Endpoints:	Primary Endpoint: Time to treatment failure, up to 12 months post-randomization.

[figure not shown]
Study Population:	118 patients ≥2 years of age in the U.S., UK, and Australia, with a history of JIA-associated uveitis or chronic anterior uveitis. Original diagnosis must have been made prior to 16 years of age (but patients can be >16 at time of enrollment). Patients must have achieved steroid-sparing control of ocular inflammation and inactive arthritis on adalimumab or a biosimilar of adalimumab for ≥12 consecutive months. Patients may not have used systemic corticosteroid or ocular corticosteroid injection within the last 180 days and must be on ≤2 drops daily of 1% prednisolone acetate with stable dose for ≥90 days. The dose of adalimumab must be stable for ≥180 days and should be no greater than 40mg biweekly for patients ≥30kg and 20mg biweekly for patients <30kg. If on a concomitant antimetabolite, dose must be stable for ≥90 days and ≤25mg weekly for methotrexate, ≤3g daily for mycophenolate mofetil, ≤250 mg daily for azathioprine, or ≤ 20 mg daily for leflunomide.
Phase:	IV
Enrollment Centers:	10 centers in the U.S., 9 in the UK, and 1 in Australia. Additional sites may be added during the study to facilitate enrollment.

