5 STUDY POPULATION

5.1 INCLUSION CRITERIA

To be eligible to participate in this study, an individual must meet all of the following criteria:

- Stated willingness to comply with all study procedures and availability for the duration of the study period
- History of JIA or CAU, diagnosed prior to 16 years of age (patient may be older than 16 at time of enrollment)^a
- ≥ 2 years of age (per FDA approval for use in children with polyarticular JIA) ^b
- Formal diagnosis of JIA-associated uveitis^c or CAU^d with no other suspected etiology
- ≥ 12 consecutive months of controlled ocular inflammation ($\leq 0.5+$ anterior chamber cell, $\leq 0.5+$ vitreous haze, and no active retinal/choroidal lesions in either eye)
- ≥ 12 consecutive months of controlled arthritis verified by a pediatric rheumatologist (see **MOP Section 3.3.1** for definition of controlled arthritis) if defined as JIA-associated uveitis
- ≥ 12 consecutive months of treatment with adalimumab^e and/or a biosimilar of adalimumab^f
- ≥ 180 days on a stable dose of adalimumab or a biosimilar of adalimumab; must be biweekly dose of no greater than 20mg (if < 30 kg) or 40mg (if ≥ 30 kg)
- If on a biosimilar of adalimumab, ≥ 90 days on the biosimilar
- If on concomitant antimetabolite (injectable or oral methotrexate, mycophenolate mofetil, azathioprine, or leflunomide), dose must be ≤ 25 mg weekly for methotrexate, ≤ 3 g daily for mycophenolate mofetil, ≤ 250 mg daily for azathioprine, or ≤ 20 mg daily for leflunomide; dose and route of administration must be stable for ≥ 90 days
- If on topical corticosteroids, dose must be ≤ 2 drops prednisolone acetate 1% or equivalent per day and stable for ≥ 90 days
- Willingness to limit consumption of alcohol during the study period
- Agreement to avoid live attenuated vaccinations
- Agreement to use highly effective contraception^g for ≥ 28 days prior to screening and throughout study period (for males and females of reproductive age)
- Suitable, in the opinion of the Investigator, to continue treatment with adalimumab or placebo per regional labeling
- No contraindications to receive adalimumab as per the local Summary of Product Characteristics (SmPC)

There are no gender, race, or ethnicity restrictions for this study.

^aPatients can be older than 16 years of age at enrollment, but original diagnosis of arthritis must have been made prior to age 16 per the clinical definition of JIA

^bAdalimumab is FDA approved for use in children ≥ 2 years of age

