- The proportion of patients who achieve an improvement in JADAS-10 as defined by Horneff et al.⁹ The criteria for a significant improvement is as follows:
 - For patients with a baseline JADAS-10 value ≤ 15 , a decrease of 4.
 - For patients with a baseline JADAS-10 value > 15 and ≤ 25 , a decrease of 10.
 - For patients with a baseline JADAS-10 value > 25 , a decrease of 17.
- The proportion of patients exhibiting macular edema.

2.3.2 Specific Aim 2

Primary Outcome: The principal outcome for Specific Aim 2 will be occurrence of

treatment failure (as defined in Section 2.3.1) in the first 6 months and in the first 12 months.

Secondary Objectives

- To determine the predictors of uveitis recurrence (treatment failure by ocular inflammation recurrence as defined in Table 1)
- To determine the predictors of time to treatment failure (as defined in Section 2.3.1) with censoring at 6 months and with censoring at 12 months,
- To determine the predictors of BCVA at 6 and 12 months,
- To determine the predictors of arthritis flare occurrence (as defined in MOP Section 6.4.1) in the first 6 months and in the first 12 months,
- In patients ages 5+, to determine the predictors of CHAQ score at 6 and 12 months.

Supplemental Objectives

Additional exploratory analyses will be conducted to determine predictors of additional variables:

- Number of missed treatment doses during the first 6 months, and during 12 months,
- CVFQ score in children aged 3 to 7 years at 6 and 12 months,
- EYE-Q score in children ages 5+ at 6 and 12 months,
- JADAS-10 and JADAS-27 scores at 6 and 12 months,
- Achievement of improvement in JADAS-10 (MOP Section 6.4.1) over the first 6 months, and over the first 12 months,
- Occurrence of macular edema during the first 6 months and during the first 12 months.

2.3.3 Specific Aim 3

Primary Outcome: The primary outcome for Specific Aim 3 is achievement of corticosteroid-sparing controlled ocular inflammation at months 6 and 12 following enrollment. Corticosteroid-sparing controlled ocular inflammation is defined by meeting all of the criteria in Table 2 in both eyes:

Table 2: Criteria for Corticosteroid-sparing Controlled Ocular Inflammation
(both eyes have to meet all criteria)

Parameter	Definition
Anterior chamber cells*	≤0.5+ cell
Vitreous haze**	≤0.5+ haze
Choroid & retina	No active retinal / choroidal lesions or macular edema (CST >2 standard deviations above normal thickness or cysts in 1mm central subfield)

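### The 85% JADAS-10 improvement rate behind one secondary power statement does not fit patients who enter with inactive, controlled or no arthritis

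*SAP*

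**What the plan says.** SAP 2.3.1 defines JADAS-10 improvement in bands. The lowest band begins "For patients with a baseline JADAS-10 value" of 15 or less and asks for a decrease of 4; the two higher bands ask for 10 and 17. The outcome is listed under Aim 1 and, as a supplemental item, under Aims 2 and 3 (SAP 2.3.2, 2.3.3).

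The power statement appears once, in SAP 3.3.2.1: "Assuming that 85% of those continuing on adalimumab will have an improvement in JADAS-10 score from baseline", the plan "provides approximately 80% power to detect a difference of at least 26% in the proportion of patients achieving an improvement between treatment groups". The size used is the whole trial, "a total sample size of 118 (and 10% assumed loss to follow-up". Nothing limits the outcome to patients with JIA or to a minimum baseline score.

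On who enters, Protocol 5.1 requires at least 12 "consecutive months of controlled arthritis verified by a pediatric rheumatologist" for those classed as JIA-associated uveitis. The synopsis speaks of "inactive arthritis on adalimumab or a biosimilar of adalimumab" for the same period. Patients with CAU and no history of JIA are also eligible (Protocol 5.1, footnote d).

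**The concern.** An improvement outcome needs room to improve. This is a withdrawal trial in patients selected for quiet disease. The continuing arm stays on the drug it was already taking; the only change Protocol 4.3 describes is that under-dosed patients receive the standard weight-based dose. A rate of 85% improving by 4 points or more is hard to reconcile with that setting.

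The same SAP list allows for quiet disease elsewhere. The preceding item expects 1% of the continuing arm to have an arthritis flare by 6 months, and the next one sets the macular edema rate by reference to its absence at baseline. JADAS-10 improvement is planned without that adjustment.

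The risk lies in interpretation. A result of no difference, printed beside a claim of 80% power, could be read as evidence that stopping adalimumab leaves the joints unaffected, when few patients may have been able to register the outcome.

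**Working it through.** **Inputs**
- Continuing arm 85%, difference 26 points (SAP 3.3.2.1). The stopping arm must be 85 − 26 = 59%, since 85 + 26 exceeds 100.
- 118 patients with 10% loss: 118 × 0.9 = 106.2, so 53 per arm at 1:1 allocation.
- Test: not named for this item. The preceding one says "We assume (for sample size assessment) a test of proportions between the two randomization groups", and I carry that over.
- Significance level: "We assume an alpha of 0.05 (two sided", stated in SAP 3.3.1 for the primary calculation and assumed here.

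**Reproducing the plan's figure**

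Continuity-corrected normal approximation, with p̄ = (0.85 + 0.59)/2 = 0.72:

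power = Φ{ [ |p1 − p2| − 1/n − 1.96·√(2p̄(1 − p̄)/n) ] / √( [p1(1 − p1) + p2(1 − p2)]/n ) }

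- Corrected difference: 0.26 − 1/53 = 0.2411
- Null term: 1.96 × √(2 × 0.72 × 0.28/53) = 0.1710
- Standard error under the alternative: √((0.1275 + 0.2419)/53) = 0.0835
- Power: Φ((0.2411 − 0.1710)/0.0835) = Φ(0.84) = 80.0%

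Fisher's exact test gives 81.0%, and the uncorrected normal approximation 85.7%. The stated figure of about 80% therefore reproduces.

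**What 85% requires**

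With a score floor of 0 (assumed), a patient can meet the criterion only with a baseline of 4 or more. The share with such a baseline is an upper bound on the improvement rate. So 85% needs at least 0.85 × 53 ≈ 45 of the 53 evaluable continuing patients, CAU patients included, to enter at 4 or more and then improve. The comparison rate has about 0.59 × 53 ≈ 31 of 53 patients improving by 4 points or more after the drug is withdrawn.

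**If only a fraction f of each arm can improve**

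The documents give no value for f, so these are assumed values. The rates 85% and 59% are kept among those able to improve. With everyone in the denominator the rates become 0.85f and 0.59f at 53 per arm. With the analysis restricted to those able to improve, the rates stay the same and the arm size becomes 53f.

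| f | Rates, all patients | Difference (points) | Power, all patients (Fisher) | Power, restricted (uncorrected normal) |
|---|---|---|---|---|
| 100% | 85% vs 59% | 26 | 81% | 86% |
| 75% | 63.75% vs 44.25% | 19.5 | 43% | 74% |
| 50% | 42.5% vs 29.5% | 13 | 23% | 56% |
| 25% | 21.25% vs 14.75% | 6.5 | 9% | 31% |
| 10% | 8.5% vs 5.9% | 2.6 | 3% | 14% |

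The last two columns use different tests and should each be read downwards from the first row. If fewer than 26% of each arm can improve, the largest possible difference is below 26 points whatever the treatment does.

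**The case against.** The arithmetic is right, and the quantity that decides the matter is unknown. The documents give no baseline JADAS-10 distribution. The definition of controlled arthritis sits in the Manual of Operations, which is not supplied, and the inclusion criterion says controlled where the synopsis says inactive. Protocol 8.1 scores JADAS from ESR, physical examination and patient functioning, so a patient with quiet joints may still enter at 4 or more. Protocol 2.2 allows that arthritis in CAU may be mild and undetected. The SAP attaches a source to the 85%, a study defining improvement in JIA by JADAS, and I cannot see which patients it covered.

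All of this stands, and it rules out a stronger reading. A reader might infer that the outcome is fixed near 0% in both arms, or that it cannot apply to this population at all. The documents prove neither. They leave the 85% unsupported and implausible for this population, not impossible.

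The consequence is also limited. SAP 3.5 makes every analysis after each Aim's primary one descriptive, with 95% confidence intervals. Baseline JADAS will be tabulated by arm (SAP 2.6.3). Worsening is covered by the arthritis-flare proportion and by continuous JADAS scores. These points reduce the harm but do not justify the 80% statement, which a reader could still cite in support of a null finding.

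**Conclusion.** The concern holds as a mismatch between a planning rate and the eligibility criteria. It is not a calculation error. The stated 80% follows from 85% against 59%, but those rates presuppose that at least 85% of the continuing arm has a baseline score high enough to fall by 4 points. Nothing in the documents supports that for patients chosen for 12 months of inactive or controlled arthritis, or with CAU and no history of JIA. The claimed power should not be taken as a property of this trial.

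The size depends on an unknown. Across assumed fractions from 75% down to 10% able to improve, power over all patients runs from about 43% to 3%. This rests on a score floor of 0, on the same fraction in both arms, and on keeping the 85% and 59% rates among those able to improve.

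A reader might go on to doubt the trial's sample size or main result. The documents do not support that: the sample size comes from the time-to-failure calculation in SAP 3.3.1, and nothing else depends on this line.

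**What to change.** - Delete the 85%/26-point power statement from SAP 3.3.2.1.
- Report JADAS-10 improvement descriptively, as counts among patients with baseline JADAS-10 of 4 or more, with that denominator shown by arm. Do this wherever the outcome appears under Aims 1, 2 and 3.
- For worsening, rely on the arthritis-flare proportion and the continuous JADAS-10 and JADAS-27 analyses already in the SAP.
- Do not substitute a newly defined JADAS-10 worsening outcome as if it had been planned. Enrollment stopped on 14 February 2024, and SAP version 5 was written after unmasking. Any such addition should be labelled as post-interim, as SAP 3.1.1 does for its own February 2024 additions.

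The cost is SAP text and one extra denominator in a table. One secondary outcome becomes descriptive in what may be a small subset. The restriction by baseline score is itself a post-interim change and should be dated as such, although it uses only a baseline value.
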